An effect of Cohen's $d = 0.27$ has been observed for a digital intervention for BPD that is based on ST only (27). Given that *alivis* consists of a combination of DBT, ST, ACT, and MSC and that participants will be closely guided during the trial, we expect the observed effect to be slightly larger and assume an effect size of $d = 0.30$. In order to obtain a power of 0.80, at a two-sided significance level of 0.05, each group should have a sample size of 176. Outpatient RCTs for BPD have an average dropout rate of approximately 25% (28,29). To compensate for dropouts, we thus aim to include and randomize $N = 470$ (2×235) participants with an allocation ratio of 1:1.

d) Primary and secondary hypotheses

~~The primary hypothesis is that receiving *alivis* in addition to TAU leads to a better reduction of BPD symptoms measured with BSL-23 at T1 (three months after the start of the intervention), compared to receiving TAU only. Secondary hypotheses are (i) intervention group participants will exhibit a better reduction of depressive symptoms at T1, compared to those in the control group; (ii) a better reduction of anxiety symptoms, (iii) reduced costs caused due to the participant's BPD, (iv) higher social and work-related functioning, (v) greater mental health-related quality of life, (vi) fewer BPD symptoms (regarding all 9 BPD criteria) measured with the Borderline Personality Disorder Checklist (BPD-CL), and (vii) higher patient activation compared to those in the control group at three months.~~

~~In addition, exploratory moderator analyses will be used to determine whether certain baseline variables have an influence on the effectiveness of *alivis*. The following variables will be recorded a priori: currently attending psychotherapy, currently taking psychotropic medication, childhood trauma, and BPD symptom severity.~~

Let the mean treatment difference be defined as μ (= *alivis* + TAU minus TAU only).

For the primary endpoint, the following two-sided hypothesis is planned to be tested.

- BPD symptoms (BSL-23) at T1
 - H0: $\mu = 0$ points against HA: $\mu \neq 0$ points

For the confirmatory secondary endpoints, the following confirmatory one-sided hypotheses are planned to be tested.

- Depressive symptoms (PHQ-9) at T1
 - H0: $\mu = 0$ points against HA: $\mu \neq 0$ points
- Anxiety symptoms (GAD-7) at T1
 - H0: $\mu = 0$ points against HA: $\mu \neq 0$ points
- Costs (self-compiled cost questionnaire) at T1

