~~The GAD-7 is a self-administered patient questionnaire used as a screening tool and severity measure for generalized anxiety disorder (GAD) (37). Studies report good reliability, as well as criterion, construct, factorial, and procedural validity (38,39).~~

Costs caused due to the patient's BPD

Costs caused due to BPD will be assessed with a self-compiled instrument assessing inpatient and outpatient treatment, support from friends, family and professional services, contacts with members of the judicial authorities and public security, medication, sick leave, and physician/therapist visits during work time.

Social Functioning at T1, assessed via the Work and Social Adjustment Scale (WSAS).

The WSAS is a 5-item self-report scale to measure social functioning in regard to physical, mental and social health as well as age group referenced competence for performance. The PROM has good psychometric properties with good criterion validity, good sensitivity and strong internal consistency ($\alpha = 0.89$) (40). Individual items address work, home management, social leisure, private leisure and relationships. Each item is rated on a 9-point Likert scale from 0 = “not at all impaired” to 8 = “very severely impaired”. The total score has a range of 0-40, with lower scores denoting less disability.

~~The WSAS is a scale to measure social functioning in regard to physical, mental, and social health as well as age group referenced competence for performance. The PROM is validated for a representative German sample (40).~~

Health-Related Quality of Life at T1, assessed via the AQoL-8D score on the Assessment of Quality of Life-8 Dimensions (AQoL-8D), German version

The AQoL-8D is a health-related quality-of-life questionnaire consisting of 35 items forming eight health dimensions:

independent living, happiness, mental health, coping, relationships, self worth, pain, senses. Validation of the AQoL-8D assessing health-related quality of life showed good psychometric properties in a German patient sample, including excellent reliability (Cronbach's $\alpha = 0.96$) and construct validity (strong correlation with the SF-36, $r = .81$) (41).

~~The AQoL-8D is a self-administered questionnaire to measure quality of life in 8 dimensions (independent living, happiness, mental health, coping, relationships, self worth, pain, senses) which has demonstrated good psychometric properties in a German sample (41).~~

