~~Severity of borderline symptoms at T1, assessed via the Borderline Personality Disorder Checklist (BPD-CL).~~

~~The BPD-CL is a DSM-IV based self-report instrument to assess BPD symptoms in the previous month (42). Importantly, in contrast to the BSL-23, the BPD-CL explicitly assesses all nine DSM-5 criteria.~~

Patient activation at T1, assessed via the Patient Activation Measure (PAM-13)

The PAM13 assesses patients' active participation in their medical care using 13 items (43,44). Items are answered using a Likert scale ranging from 1 = "strongly disagree" to 4 = "agree strongly", yielding a total score between 13 and 52. The German version of the PAM13, the PAM13-G, is validated and demonstrates good psychometric properties, including a good internal consistency of Cronbach's $\alpha = 0.84$ (44). An improvement of 4 points on the PAM-13 is considered an MCID (56). Therefore, responders will be defined as patients who improve by at least 4 points on the PAM-13 from T0 to T2. The proportion of responders between groups will be compared using χ^2 tests.

~~The PAM-13 is a 13-item instrument assessing patients' active participation in their medical care (43). The German version of the PAM-13, the PAM-13-G, is validated and demonstrates good psychometric properties (44).~~

Exploratory Endpoints: Assessments listed in "Secondary endpoints" at T2/T3

Sociodemographic Variables:

- Age
- Gender

- Sex
- Education
- Employment Status
- Family Situation
- Language ability
- Ethnicity

Clinical Variables:

Assessed at T0 only:

- First diagnosis (date)
- Inclusion diagnosis (BPD) using the respective section of the SCID-5-PD interview (45)
- Psychiatric comorbidities (via Mini-DIPS) (46)
- Psychotherapy (past, type)

Assessed at all timepoints (T0-T3):

- Medications (name of medication, dose, frequency)
- Psychotherapy (current, type)
- Childhood trauma (via Childhood Trauma Questionnaire (CTQ; 47,48))
- Number of BPD-related hospitalizations (T0: past 12 months, T1-T2: past 3 months, T3: past 6 months)
- Number of hospitalizations due to other reasons (T0: past 12 months, T1-T2: past 3 months, T3: past 6 months)
- Number of days in sick leave (past 3 months)
- Number of days in sick pay (past 3 months)
- weight and height (current)
- Use of any other online program for BPD (T0: lifetime, T1-T2: past 3 months, T3: past 6 months; name)

Treatment satisfaction:

- Program Evaluation of the Program (NPS, Net Promoter Score) (49)

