Moreover, responder analyses will be conducted. Unless a specific MCID is specified for an endpoint in section 6.1d), responders will be defined by reaching the cut-off of 15% of the range of the scale (64). ~~the reliable change index (RCI; 33) will be used to identify responders to treatment in patients with complete observations. The RCI is calculated as the ratio of the difference between pre- and post-scores of an individual participant (numerator) and the standard error of measurement of the difference (denominator). RCI scores larger than 1.96 indicate that it is unlikely that the posttest score is not reflecting real change ($p < .05$), thus indicating that the participant is a responder (33).~~ If a specific MCID is specified for an endpoint, responder analyses will instead be based on that value. Responders will then be defined as participants reaching this difference from T0 to T1. Additionally, exploratory responder analyses will be conducted for each endpoint, where response is defined as 50% improvement since baseline. The proportion of responders between groups will be compared using χ^2 tests. Moreover, the odds ratio will be reported.

d) Significance level and power

significance level (α) = 0.05 (two-sided)
power = 0.80

e) Sample size

1) Clinical data on outcome variable and effect size

An effect of Cohen's $d = 0.27$ has been observed for a digital intervention for BPD that is based on ST only (27). Given that *alivis* consists of a combination of DBT, ST, ACT, and MSC and that participants will be closely guided during the trial, we expect the observed effect to be slightly larger and assume an effect size of $d = 0.30$. In order to obtain a power of 0.80, at a two-sided significance level of 0.05, each group should have a sample size of 176. Outpatient RCTs for BPD have an average dropout rate of approximately 25% (28,29). To compensate for dropouts, we thus aim to include and randomize $N = 470$ (2×235) participants with an allocation ratio of 1:1.

2) Expected outcomes across treatment groups

See 5. d.

3) Adjustments due to pre-planned interim analyses

An interim analysis is planned after three months (T1; primary time point). There will be no adjustments.

4) Effect size and non-inferiority margin

See 7. e 1).

5) Randomization allocation ratio

1:1, in variable blocks of 4, 8, or 16 participants each ~~no block randomization, no stratification~~

6) Expected drop-out rate

25% (28,29).

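### The exploratory 50%-improvement responder rule cannot be met on PAM-13 from a baseline of 35 upwards, and the default 15%-of-range rule gives no threshold for costs

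*Combined protocol and SAP*

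**What the plan says.** Section 7.c sets out two layers of responder analysis, both compared by χ² test with an odds ratio.

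- Main layer: where no MCID is given for an endpoint, "responders will be defined by reaching the cut-off of 15% of the range of the scale". Where one is given, it takes over: "If a specific MCID is specified for an endpoint, responder analyses will instead be based on that value".
- Additional layer: "exploratory responder analyses will be conducted for each endpoint, where response is defined as 50% improvement since baseline". The text gives no exception, formula or direction of scoring.

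Section 6.1.c describes PAM-13 as 13 items scored 1 to 4, "yielding a total score between 13 and 52", with a 4-point improvement as its MCID. Costs appear in section 5.d among the confirmatory secondary endpoints as "Costs (self-compiled cost questionnaire) at T1", with the hypothesis stated in euro. Section 6.1.c adds that "Costs caused due to BPD will be assessed with a self-compiled instrument assessing inpatient and outpatient treatment" and lists further cost items, but it gives no minimum, maximum, MCID or responder definition for costs.

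**The concern.** A percentage-of-baseline rule suits a scale that starts at zero and on which lower is better, because every non-zero baseline can then be halved. PAM-13 has neither property: it starts at 13, is bounded at 52, and improvement moves towards the bound. Followed literally, the rule classes some participants as non-responders at randomisation, whatever happens to them afterwards.

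The cost problem is of another kind. The 15% rule belongs to the main responder layer, not the exploratory one, and it falls on costs by default because no MCID is given. A euro amount has no scale range, so the rule yields no threshold.

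At stake are the PAM-13 responder table under the 50% rule and the cost responder table under the 15% rule. If the rules stay as they are, someone must choose a formula at the analysis stage or report a deviation under section 7.o. Section 7.c keeps the principal investigator blinded only until the primary outcome and the main safety outcome have been analysed, so blinding is not secured for such later choices.

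**Working it through.** **The plan's own figure.** Section 6.1.c gives the BSL-23 cut-off as 0.6 points. The formula is 0.15 × (maximum − minimum) = 0.15 × (4 − 0) = 0.6, which agrees.

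**The 15% rule on the other endpoints without an MCID** (ranges from section 6.1.c):
- GAD-7, 0 to 21: 0.15 × 21 = 3.15.
- WSAS, 0 to 40: 0.15 × 40 = 6.0.
- AQoL-8D: no score range stated, so not computable from the documents.
- Costs: no minimum or maximum stated, and a euro amount has no inherent one, so there is no threshold.

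PHQ-9 (5 points) and PAM-13 (4 points) have MCIDs and do not use this rule. For comparison, 15% of the PAM-13 range would be 0.15 × 39 = 5.85.

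**The 50% rule on PAM-13.** A gain of 50% over baseline b needs 1.5 × b ≤ 52, so b ≤ 52/1.5 = 34.67.

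| Baseline | Score needed | Gain needed | Room to 52 |
|---|---|---|---|
| 13 | 19.5 | 6.5 | 39 |
| 26 | 39 | 13 | 26 |
| 34 | 51 | 17 | 18 |
| 35 | 52.5 | 17.5 | 17 |
| 40 | 60 | 20 | 12 |

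Whole-number totals run from 13 to 52, which is 40 values. Those from 35 to 52, which is 18 values, cannot meet the rule. At a baseline of 34 the required gain is 17/4 = 4.25 times the MCID.

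**Effect on the comparison.** Let f be the share with a baseline of 35 or more, equal in expectation in the two arms because allocation is randomised 1:1. Let p1 and p0 be the response rates among those who can respond. The observed rates are (1 − f)p1 and (1 − f)p0. If p1 = p0, the observed rates are equal too, so the ceiling creates no group difference. If they differ, the observed difference is (1 − f)(p1 − p0), which is smaller.

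**Size of f.** The documents give no PAM-13 baseline distribution. As an assumption only, take a normal distribution and a cut at 34.5:
- mean 30, SD 4: z = 1.125, f about 13%;
- mean 34, SD 6: z = 0.083, f about 47%;
- mean 40, SD 4: z = −1.375, f about 92%.

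The range is too wide to say anything about this trial.

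**The 50% rule on costs.** Follow-up cost ≤ 0.5 × baseline cost is well defined for any baseline above 0 euro. At 0 euro the percentage change is undefined and no improvement is possible.

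**The case against.** The best defence is that little depends on these rules. The 50% analysis is labelled exploratory and comes on top of the main one. PAM-13 keeps its 4-point responder analysis and stands last in the gatekeeping order. Every primary and secondary endpoint, costs included, has an ANCOVA estimate with a 95% CI. All of that stands, and it settles the priority.

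A second defence is that 50% improvement could be counted in another way. Counted from the floor of 13, the condition is 13 + 1.5 × (b − 13) ≤ 52, which moves the limit only to b = 39 and lets a participant at 13 respond with no gain. Counted as half the distance to 52, it is always reachable. At a baseline of 36 the three readings ask for 18 points (impossible), 11.5 and 8. The plan states neither alternative, so this confirms the gap.

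A reader might also infer more than the documents support:

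- *That the PAM-13 test mainly reflects who started low.* Randomisation balances the unreachable baselines in expectation. The loss is in sensitivity and interpretability.
- *That a required gain growing with baseline is itself the fault.* BSL-23 does the same: 0.5 × 1.07 = 0.535 at the entry cut-off and 0.5 × 4 = 2.0 at the top. Only the ceiling is particular to PAM-13.
- *That neither rule works for costs.* The 50% rule fails only at a baseline of 0 euro. The share at zero is unknown, and having no treatment does not imply zero cost, since the instrument also counts sick leave and support from family. PHQ-9, GAD-7 and WSAS can also be zero at baseline.
- *That one very expensive participant would set the cost threshold.* This would need the observed range to be used, and the plan does not propose that.
- *That AQoL-8D has the same ceiling.* Its score range and direction are not stated, so this cannot be shown.

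**Conclusion.** Two responder rules in section 7.c fail when followed as written. On the PAM-13 raw total, the only scoring that the documents give, and with improvement taken as a percentage of the baseline score, response under the 50% rule is impossible for 18 of 40 possible baselines. That count describes the scale and is not a share of participants, which remains unknown. The resulting proportions are hard to interpret and the comparison is less sensitive, without bias between arms. For costs, the 15% rule has no value; the 50% rule is usable above 0 euro.

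The PAM-13 ceiling and the missing cost threshold need no assumption beyond the stated scoring. The primary analysis, the confirmatory ANCOVA tests, the sample size and the PAM-13 MCID responder analysis are unaffected. This is a low-priority correction, worth making before the data are analysed.

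**What to change.** Amend section 7.c as follows.

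- Limit the 50% rule to the scales that start at zero with higher scores worse: BSL-23, PHQ-9, GAD-7 and WSAS.
- For PAM-13, use only the 4-point MCID responder. Section 6.1.c defines it from T0 to T2 while section 7.c refers to T0 to T1, so name the time point in the same edit.
- For AQoL-8D, state the scoring range and direction and use the 15% rule only, unless the 50% rule is shown to be reachable on that scoring.
- State that the 15% rule does not apply to costs, and report the mean difference in euro with its 95% CI.

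The cost is a few sentences and a few exploratory responder tables: the 50% tables for PAM-13, AQoL-8D and costs. The cost table under the 50% rule is computable above 0 euro; if the sponsor wants to keep it, the handling of a zero baseline must be stated. Section 9 requires approval by the principal investigator and the sponsor, notice to the ethics committee and a registry update. Data collection, sample size and confirmatory testing do not change.

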The primary time point for collecting data on the effectiveness of the intervention will be 3 months post allocation (T1). Six months post allocation (T2) and 12 months post allocation (T3) will be other time points for data collection, which will be treated as follow-ups to test the stability of effects. A first analysis is planned after the last patient completes T1. The complete data set will be open for analysis after the last patient completes T3. Participants will receive a 10€ voucher from www.wunschgutschein.de as an incentive for participating in T1, T2 and T3 each (max. 30€). All participants (from the intervention and control group) will receive this compensation if they complete the follow-up questionnaires, and, in particular, the compensation in the intervention group will not depend on the actual use of *alivis*. Details of data collection and analysis are summarized in Figure 1 and Table 1. The expected total duration of the study for each participant is 14 months (1 month pre-assessment, 12 months intervention phase, up to 1 month reminders for the last assessment). The expected total duration of the entire study including recruitment is estimated at 24 months.

e) Equipment for assessing the clinical investigation variables

Equipment is limited to online surveys of participants using a German provider for surveys including clinical trials, LimeSurvey. PROMs are listed under 6.1 c-d.

f) Replacement of subjects

Not applicable.

g) Investigation sites

The study is designed as an online trial; there will be no traditional physical investigation site(s). See 1.4 b and 6.1 e.

h) Completion of the clinical investigation

Data acquisition of the trial will be completed 12 to 13 months after the last patient in (up to one month buffer for reminders to complete T3). Complete analyses of the dataset will denote completion of the investigation.

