f) Procedures to be performed by user and analysis

Not applicable.

g) Pass/fail criteria

Not applicable.

h) Interim analysis and criteria for termination

Dataset will be open for interim analysis after the last patient completed T1. Results of the interim analysis will have no consequences for further study conduct.

i) Management of bias

Accompanying clinical variables of the participants are recorded at baseline, post-treatment (T1) and follow-up (T2, T3). It is conceivable that differences in e.g., the concomitant therapy in both groups in the course of the study could influence the study result. The observation period is chosen so that both the intended and unexpected effects of the program can be assessed with validity.

j) Management of potential confounding factors

The result of the study could be influenced by a number of confounders (e.g., age, gender, therapy, etc.). By randomizing the participants to the intervention or control group, roughly equal distribution in both groups can be assured, so that possible differences between groups can be attributed to the intervention. Additionally, potential differences in baseline values in the outcome variables of interest will be controlled for by including them as covariates in ANCOVA.

k) Multiplicity control and adjustment of error probabilities

No adjustment of the significance level α of 0.05 (two-sided) given that a gatekeeping testing strategy will be applied as suggested by the FDA (65). The secondary endpoints (listed in section 6.1.c) are listed in priority order for that approach.

l) Subgroups for analysis

The following subgroup analyses are planned:

- a) effectiveness of *alivis* depending on sex (male, female, intersex);
- b) effectiveness of *alivis* depending on gender (male, female, diverse);
- c) effectiveness of *alivis* in patients with concomitant psychotherapy at baseline compared to those without;
- d) Effectiveness of *alivis* in patients who take psychotropic medication (ATC codes N05, N06) at baseline compared to those who do not;
- e) Effectiveness of *alivis* in patients with changes in treatment (i.e., psychotherapy or regular psychotropic medication) between baseline and T1 vs. patients without changes in treatment;
- f) Effectiveness of *alivis* in patients with previous diagnosis of BPD vs. in patients who were initially diagnosed with BPD as part of the study.

Results of these subgroup analyses will be visualized as a table and forest plot.

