m) Missing, unused or spurious data, including drop-outs

In the ITT analysis, missing data points will be imputed using the respective variable values at baseline as well as group membership and other sociodemographic and clinical variables (~~such as~~ age, sex, education, employment, family status, psychotherapy at baseline, psychotherapy ever). The ITT analysis will be implemented following a computationally efficient implementation for bootstrapped maximum likelihood multiple imputation (67,68) by von Hippel and Bartlett (2021) using the *R* packages *bootImpute* (68) and *mice* (69). In detail, 1,000 bootstrap samples of the incomplete dataset will be generated for each outcome variable and then the relevant outcome variable will be imputed twice with the *mice* package with default settings (i.e., using predictive mean matching with a pool of 5 candidate values) as recommended.

n) Exploratory analysis and sensitivity analysis

Exploratory moderator analyses will determine the influence of certain baseline variables on the effectiveness of *alivis*. The following variables will be established a priori: currently attending psychotherapy, BPD symptoms (BSL-23), and patient activation (PAM-13).

Reference-based sensitivity analysis ('jump to reference' (63,68,70)) will be applied following procedures for the ITT-analysis, using an implementation for the *R* programming environment. Assumptions about the structure of missing data points will be tested in advance.

o) Reporting of deviation(s) from original statistical analysis plan

If there are deviations from the original statistical planning, this deviation will be stated in the study register, study report and the publication as well.

p) Handling potential imbalance of numbers of subjects across investigation sites

Not applicable.

q) Strategy for pooling data

Not applicable.

r) Estimand strategy

The treatment policy estimand will be used to handle any potential intercurrent events. In this study, intercurrent events are defined as the initiation or discontinuation of psychotherapeutic or psychotropic treatment and the discontinuation of *alivis* usage for any reason in the intervention group. The treatment policy estimand evaluates the treatment effect for all randomized patients, irrespective of their use of *alivis* or specific elements of TAU.

The following estimand strategy attributes are defined:

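### With 1,000 bootstrap samples, a borderline primary p-value (roughly 0.04 to 0.07) can fall on either side of 0.05 by random seed alone; 10,000 or more would be a cheap improvement

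*Combined protocol and SAP*

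**What the plan says.** Section 7.c makes the multiply imputed ITT ANCOVA the primary analysis, comparing T1 scores between groups with the baseline score as covariate. Section 7.m sets how the imputation and its variance are obtained: "1,000 bootstrap samples of the incomplete dataset will be generated for each outcome variable and then the relevant outcome variable will be imputed twice", with predictive mean matching from five candidate values. Section 7.d sets "significance level (α) = 0.05 (two-sided"). Section 7.k leaves alpha unadjusted, "given that a gatekeeping testing strategy will be applied", so each confirmatory test is a yes/no step and the secondary endpoints follow in priority order. The current text names no random seed and sets no tolerance for Monte Carlo error.

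**The concern.** When one bootstraps first and imputes second, the standard error is not computed by formula from a single data set. It is estimated from the spread of the treatment effect across the bootstrap samples, and the point estimate is an average over the same draws. Both carry random error that comes from the computer and not from patients, and that shrinks only as the number of samples grows.

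This matters because the result feeds a hard threshold. If BSL-23 misses 0.05, the six secondary endpoints listed in section 5.d cannot be tested as confirmatory. For a result near the threshold, that decision could turn on the seed, and an independent rerun of the same data could contradict the report.

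**Working it through.** **The plan's own figure.** Section 7.e says "assume an effect size of $d = 0.30"$ and that "each group should have a sample size of 176". With the normal approximation, n = 2 × (1.96 + 0.8416)² / 0.30² = 174.4, so 175; the t-test version gives 175.4, so 176. Allowing for 25% dropout, 176 / 0.75 = 234.7, so 235 per group and 470 in all. The sample size reproduces. The documents give no figure for Monte Carlo error.

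**Inputs from the documents.** 470 participants in two arms, 25% dropout, B = 1,000 bootstrap samples, M = 2 imputations, predictive mean matching with 5 donors, baseline-adjusted ANCOVA, two-sided 0.05.

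**Assumptions not in the documents.** T0-T1 correlation 0.6; missing T1 data also varied to 15% and 35%; in those runs, only group and baseline score as imputation predictors.

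**Method.** One simulated data set was held fixed and analysed again with many seeds. Pooled variance = (1 + 1/B)(MSB − MSW)/M + MSW/(BM), where MSB and MSW are the between- and within-bootstrap mean squares.

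**Seed variation at B = 1,000, M = 2** (100 seeds each):

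| Missing | Mean p | Range of p | Seeds with p < 0.05 | SD of z or t |
|---|---|---|---|---|
| 15% | 0.048 | 0.030–0.064 | 65% | 0.064 |
| 25% | 0.056 | 0.035–0.077 | 21% | 0.061 |
| 25% (second data set) | 0.055 | 0.037–0.073 | 23% | 0.057 |
| 35% | 0.063 | 0.043–0.086 | 5% | 0.057 |

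A separate run (60 seeds, 25% missing) gave an SD of z of 0.060.

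**Why about 0.06.** The relative SD of the standard error is about 1/√(2 × df). With df about 756, that is 2.6%; the simulations gave 2.3% to 2.7%. For the second 25% data set, the standard error contributes 1.925 × 0.0266 = 0.051 to the SD of the statistic and the point estimate 0.0026 / 0.0892 = 0.029. Together √(0.051² + 0.029²) = 0.059. Near p = 0.05 the SD of p is 2φ(1.96) × 0.06 = 0.117 × 0.06 = 0.007.

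**Where it bites.** With an SD of 0.061, z within 1.96 ± 1.96 × 0.061 corresponds to p from 0.038 to 0.066. Away from that band flips are rare: at mean p 0.032, 99% of seeds passed; at mean p 0.005, all did.

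**How often two seeds disagree.** Let z ~ N(δ, 1) be the result free of seed noise and s the seed SD. Integrating 2q(1 − q) over z, where q is the chance that a seed passes, gives approximately (2/√π) × s × φ(δ − 1.96).

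- Stated power: δ = 0.30 × √(176/2) = 2.81, taken as 2.8. With s = 0.06: 1.128 × 0.06 × φ(0.84) = 1.9%.
- ANCOVA with correlation 0.6 (simulated SE 0.086): δ = 0.30 / 0.086 = 3.49, about 94% power. 1.128 × 0.06 × φ(1.53) = 0.84%.
- Ceiling, if the true effect sits exactly at the threshold: 1.128 × 0.06 × φ(0) = 2.7%.

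The chance that the data land in the sensitive band at all is about 6.7% at δ = 2.8 and about 3% at δ = 3.49.

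**With B = 10,000.** The seed SD of z falls to 0.018, and disagreement to 0.57% (δ = 2.8) and 0.25% (δ = 3.49). On one fixed data set the SD of p fell from 0.0066 (range 0.034–0.068, 200 seeds) to 0.0021 (range 0.044–0.053, 60 seeds).

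**Role of the two imputations.** At B = 1,000, raising M from 2 to 10 or 50 moved the SD of p only from 0.0066 to 0.0056 or 0.0054.

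**Error rates.** Seed noise adds 0.06² = 0.0036 to a variance of 1. Two-sided type I error moves from 0.0500 to 0.0504, and power at δ = 2.8 from 79.95% to 79.91%.

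**The case against.** The best counter-argument is that this noise hardly matters. It causes no bias, leaves error rates where they were, and touches only results that nobody should read as clear-cut. The simulated data sets in the table were placed close to the threshold on purpose, so their pass rates say nothing about a typical trial. All of that stands, and it sets the priority.

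A second objection is that 10,000 samples do not abolish the effect: data sitting on the threshold can still fall either way, and a fixed seed alone would make the reported decision reproducible. That is also true. But a seed makes the answer repeatable without making it more precise; only more samples do that. Section 7.m describes its settings as recommended in cited methods papers, which are not available here. Whatever they advise, the variation calculated above follows from B = 1,000.

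Three stronger readings are tempting and should be resisted.

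- A reader might infer that the T1 hypothesis will be tested twice with different draws, because section 7.e says "An interim analysis is planned after three months (T1; primary time point") and section 6.1.d says "The complete data set will be open for analysis after the last patient completes T3". No section says that T1 is retested. Section 7.c tests T2 and T3 separately as prolonged effects, and the imputation predictors listed in 7.m include no T2 or T3 data, so nothing calls for imputing T1 again.
- A reader might blame the two imputations. The calculation shows that they are a minor contributor.
- A reader might conclude that type I error is inflated. For a single run it is not, to any material degree.

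**Conclusion.** The point holds as a low-priority precision issue. With 1,000 bootstrap samples the seed moves z by about 0.06 (SD) and can decide the gate when p is roughly 0.04 to 0.07. Under the planned effect, two seeds would disagree on the primary test in about 0.8% to 1.9% of trials, against about 0.25% to 0.6% with 10,000 samples. The lower end of each range rests on the assumed T0-T1 correlation of 0.6; the upper end takes the stated 80% power at face value. A higher correlation at the same effect would lower the figures further. The seed SD of p stayed between 0.0066 and 0.0079 in all the 1,000-sample runs near 0.05 with 15% to 35% missing data; the correlation was not varied in those runs. The documents do not support a claim of bias, inflated type I error, lost power or a second T1 test.

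**What to change.** In section 7.m, replace 1,000 by at least 10,000 bootstrap samples for each confirmatory outcome, and allow for more if the p-value is close to 0.05 and the Monte Carlo error is still material. For scale, scaling by 1/√B puts the SD of p near 0.05 at about 0.117 × 0.06/√50 = 0.001 with 50,000 samples. Record a pre-specified random seed in the same sentence. Two imputations per sample can stay.

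The cost is one sentence and computing time for a data set of 470 rows. Participants, data collection and the estimand are unaffected.
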